## 8) Study Timelines\*

Both conditions will be tested as 16-week interventions. There will be an additional 8-week period of continuing care, then 6 months of no contact, followed by a final assessment. The final assessment will occur 12 months after baseline. The duration of an individual subject's participation in the study will be 1 year (including all follow-up assessments).

The duration anticipated to enroll all study subjects is 35 months. Recruitment will begin in month 8 of the study and end in month 43.

The estimated date for the investigators to complete this study (including primary analyses) is 60 months.

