phase the CIFFTA families will have the opportunity to interact with the therapist via the website for a period of 8 additional weeks and can access all website resources. To match dosage time during aftercare, TAU will receive telephone calls in which the therapist asks how things are going and reiterates some of the main messages of treatment. The participation of adolescents and families in clinical services and final assessments will end around month 54 of the study. Months 55-60 will focus on data cleaning and logic checks, data base locks, and the analysis, interpretation and reporting of findings. Assessments will be conducted at baseline, 16 weeks post baseline/treatment termination, and at T3: 6 months post completion of continuing care. Assessments will be collected in person or virtually via HIPAA compliant Zoom. Data from self-reported satisfaction with the intervention, youth outcomes, and service utilization outside of the program will be collected throughout the course of therapy.

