will be contacting them within 48 hours. These activities are conducted by study personnel (UM researchers) at the UM site, the IIFC or virtually via HIPAA compliant Zoom. If a participant is randomized to the control condition, a warm hand-off process will be used to connect the family to an agency staff member for the treatment. If a referral is identified by the Nicklaus Children's Hospital Inpatient Psychiatry Department staff, they will contact the youth's caregivers directly to explain the study. If the family is interested in participating in the study, the Nicklaus staff will obtain a release of information so that the UM staff can contact the youth and caregiver to sign consent, screen and assess the family. If the family is not randomized to the CIFFTA program, the UM staff and the Nicklaus staff will work together to place the youth in an outpatient program in the community. Nicklaus Children's Hospital will not be releasing any information to the UM CIFFTA program. All participants will be assessed again 16 weeks post baseline/treatment termination, and at T3: 6 months post completion of continuing care (12 months after baseline). Bachelor's/Master's level research assistants who are bilingual in English and Spanish will be available to administer all assessments. Each assessment interview lasts approximately 2 hours and consists of two parts, an interview (adolescents and parents separately) and responding to questions on the REDCap. The assessor interviews parents while the adolescent completes the REDCap battery and then they switch. The Measures appendix provides an overview of the measures, the time-points and the target of data collection. To increase participation families will be paid \$75 for T2 and \$100 for T3 completed assessments. They will receive the money either in person or cash deposits via Zelle. The fees may be slightly higher than studies that work with only one participant. The fee is meant to compensate 2-3 participants (typically adolescent and two caregivers) for 2 hours of assessment time. Interview data are entered directly into the REDCap system. In addition to the baseline assessment that all families receive at the start of the study, families will be asked to participate in an additional semi-structured interview right after the baseline (1 hour semi-structured interview for the child and 1 hour for the parent/caregiver). This interview is voluntary and asks additional qualitative questions about family functioning and self-harm to gather details on these concepts (these types of questions are asked in the baseline and follow-up assessments). To compensate for each family's time participating in these interviews, each youth will be offered a \$15 gift card to either Target or Amazon and each parent/caregiver will also be offered a \$15 gift card to either Target or Amazon.

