Treatment for Adolescents (CA CIFFTA).CA CIFFTA will consist of a hybrid intervention utilizing some Office Based CIFFTA sessions and some technologydelivered material (e.g., psycho-educational modules and the collect of information on risk patterns and situations). CIFFTA will be delivered in person or virtually via HIPAA compliant Zoom. During the treatment phase CIFFTA participants will be offered 1. 5 hours of contact per week that includes 45 minutes of face-to-face time per week plus approximately 45 minutes of intervention time delivered via the web over 16 weeks. During the 8 week continuing care phase participants will continue to access the website and its resources and will receive targeted messages focused on how to handle the conditions found in T2 that might be expected to fuel relapse (family or interpersonal conflicts and continuing depression). CA CIFFTA will: 1) deliver psycho-educational modules (e.g., depression, risky sexual behavior information, emotion regulation and distress tolerance, handling marginalization, coping strategies for traumatic experiences) via multimedia formats that include text, audio, video and graphics,2) facilitate contact with the counselor via computer-based messaging, 3) collect diary-card type information (e.g., affective struggles, high risk environmental cues) to be used in treatment, 4) document usage of all website components, and 5) facilitate continuing care (post-treatment) checkups to prevent relapse. Many of the videos originally created for the original CA-CIFFTA (e.g., psycho-educational material on adolescent depression, substance use risk, risky sexual behavior, and others offered in both English and Spanish) will be updated/enhanced. As in the pilot, parents and adolescents will watch videos and click the symptoms of concern to them. This information will be automatically transmitted to therapists and used in the next session.

	Family Sessions		Adolescent Sessions	
	Treatment	Psycho-educational Modules (M= Mandatory O= Optional)	Treatment	Psycho-educational Modules
Early Stage	-Engage family members -Assess family History -Identify core family themes -Tailoring treatment -Motivational Interviewing	-Co-occurring adolescent disorders (M) -Parenting Module (M) -Health Promotion (M)	-Engage adolescent -Motivational interviewing -Goal Identification -Tailoring treatment	-Co-occurring disorders(M) -Health Promotion (M)

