Adaptations for youth who report being LGBTQ and/or exposed to trauma, and families. CIFFTA's design lends itself to adaption to diverse populations. Its logic and emphasis on tailoring facilitates the treatment's extension to new populations with unique stressors. During the development phase of this study (first 7 months) we will build on existing modules. Some of the expected adaptations will focus on modules for kids on how they can cope with stressors related to LGBT-related rejection and alienation, emotion regulation and distress tolerance for ameliorating self-harm behaviors, using evidencebased coping strategies for risk factors result from exposure to traumatic events (see Seeking Safety strategies). A module for parents who are having a hard time accepting their son's/daughters being a gender/sexual minority youth will help them to understand the normative stages some parents must go through, allow parents to express their concerns, distress, and fears, so that they are more ready to have a productive family therapy session with their sons and daughters. A parallel module may be offered to youth to increase their readiness to have a family session in which a loving and caring relationship can be created.

Measures: Measures have been selected for: 1) Screening; 2) Ultimate Adolescent Outcomes, e.g., Self-harm; 3) Immediate Outcomes, e.g., depression, emotion regulation, family conflict, and substance use; 4) Cultural Factors; and 5) Additional Measures, e.g., trauma, minority stress. Measures will be administered at Screening, Baseline (T1) 4 months after baseline (Termination or T2), and 12 months after baseline (T3). Spanish versions of the measures are available. Every effort has been made to reduce participant burden. The total battery is expected to take 90 minutes to administer to youth and 40 minutes to parents. These will be administered in person or via HIPAA compliant Zoom. Measures are attached.

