## 23) **Prior Approvals**

This study was approved by the IRB on 09/01/2017 for an NIH "Just in Time" request.

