Lastly, to examine whether changes on the plausible mechanisms of action was associated with the likelihood of engaging in self-harm in the past month at termination in the full sample; after controlling for gender and LGBTQ status, a series of hierarchical logistic regressions were performed. With only two timepoints we could not conduct formal analyses of mediation, but we could explore whether the patterns of change were consistent with plausible mediators. In these models, self-harm in the past month was the binary outcome variable, LGBTQ status and gender were entered in Step 1 as covariates, and the proposed mechanism of action (i.e., depression, parent communication, family connectedness, and emotion regulation) were entered in Step 2.

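### Self-harm, the only primary endpoint, gets no inferential comparison between arms at any time in the SAP, and the scheduled 12-month assessment (T3) is not accounted for

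*SAP*

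**What the plan says.** **Assessment schedule.** Protocol section 10 (Screening and Assessment Procedures) states: "All participants will be assessed again 16 weeks post baseline/treatment termination, and at T3: 6 months post completion of continuing care". The Measures paragraph of the same section puts T2 at 4 months and T3 at 12 months after baseline. Section 8 describes what follows the 16-week treatment: "There will be an additional 8-week period of continuing care, then 6 months of no contact, followed by a final assessment".

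**Aim and endpoint.** Aim 2 (section 3) is preliminary efficacy in reducing self-harm, and in changing its risk factors, against Treatment-As-Usual (TAU). Section 9 lists self-harm as the sole primary endpoint and attaches no timepoint to it.

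**SAP.** The attrition models concern reaching termination and T2. Depression, emotion regulation and family connectedness are analysed by mixed ANOVA, and talking to parents by chi-square tests; both are described only as change over time. Self-harm and suicidal thoughts are summarised descriptively at baseline and termination by condition, and suicidal thoughts are then also tested between arms. The last paragraph models past-month self-harm at termination on gender, LGBTQ status and a candidate mechanism, and explains: "With only two timepoints we could not conduct formal analyses of mediation". T3 is not mentioned anywhere.

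**The concern.** Two gaps meet here. First, the SAP as written produces no p-value, interval or model coefficient that compares the arms on self-harm, so Aim 2 has no inferential result on its own primary endpoint. Second, one of three scheduled assessments is missing from the SAP without explanation. A reader cannot tell non-collection, deferral to another report and omission apart, and these mean different things for how the results should be read.

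The continuing-care phase makes the second gap matter. It is meant to "facilitate continuing care (post-treatment) checkups to prevent relapse", and it begins after T2. If the analyses stop at T2, nothing stated reflects outcomes after that phase. T3 would test the whole programme at 12 months, not continuing care by itself. Adverse events are queried at T3, but section 9 says the study has no safety endpoints, so that monitoring does not replace an arm comparison of self-harm.

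**Working it through.** **1. Timepoints, side by side.** Protocol: T1, T2 and T3, three outcome assessments. SAP: baseline and termination/T2, two. T3 is the one not accounted for. The protocol's own timing is coherent: 16 + 8 = 24 weeks, about 5.5 months, and adding 6 months gives about 11.5 months, in line with the stated 12.

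**2. Was T3 planned for late enrolees?** Section 8 says "Recruitment will begin in month 8 of the study and end in month 43". Month 43 + 12 = month 55. Section 10 says "The participation of adolescents and families in clinical services and final assessments will end around month 54 of the study". Both fall inside the planned 60 months, so T3 was intended for everyone. This shows intention only, because no actual assessment dates are given.

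**3. Every use of self-harm in the SAP.**
- Rates at baseline and termination by condition: descriptive only.
- Mechanism models: self-harm is the outcome, but the listed terms are gender, LGBTQ status and the mechanism. There is no term for arm, so no coefficient compares the arms.
- The chi-square test by condition in the same paragraph as the rates is for thoughts of suicide.

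Inferential arm comparisons of self-harm: none.

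**4. What a self-harm contrast could deliver.** The documents give no TAU rate, effect size or completer count, so the following are assumptions: TAU proportion p0 = 35–55%, odds ratio 0.3–0.7, equal allocation of 100, and m completers per arm. The case m = 50 is no loss. The case m = 35 is 70% of 50; the 70% is the adolescent assessment rate at 16 months in the earlier trial described in section 10.

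95% CI half-width = 1.96 × √[p0(1−p0)/m + p1(1−p1)/m]

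| m per arm | Half-width, points |
|---|---|
| 50 | 16.3–19.5 |
| 35 | 19.5–23.3 |
| 25–30 | 21.1–27.6 |

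Example: p0 = 0.45 and OR 0.4. The odds are 0.818 × 0.4 = 0.327, so p1 = 0.247 and the difference is 20.3 points. The half-width is 18.2 with m = 50 (interval 2.1 to 38.5) and 21.8 with m = 35 (−1.5 to 42.1).

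For scores, half-width in SD units = 1.96 × √[(2/m)(1−r²)], with r the correlation with baseline. For r from 0.5 down to 0 it is 0.34–0.39 with m = 50 and 0.41–0.47 with m = 35.

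**5. Missing data.** With 30% missing in each arm, the difference is 0.7 × observed + 0.3 × (x1 − x0), where x1 and x0 are the unseen proportions. As x1 − x0 runs from −1 to 1, the worst-case bounds span 0.3 × 2 = 60 points. Any estimate then leans on missing at random.

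**The case against.** The strongest reply is that nothing is breached except a schedule. The primary endpoint has no timepoint, no aim mentions 12 months, the efficacy aim is preliminary, and the documents contain no T3 analysis that was promised and then removed. The SAP is written in the past tense, a T3 contrast would be post hoc and imprecise, and T3 data may not exist. On that view only a sentence on T3's status is needed. This stands as a limit on the T3 part, where the remedy must be conditional. It does not answer the self-harm part: the T2 contrast does not depend on T3, and Aim 2 has no inferential result on its endpoint without it.

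Several stronger readings are tempting, and the documents do not support them:
- *The whole SAP declares two timepoints.* The sentence explains why mediation was not tested in the mechanism models. That the mixed ANOVAs and parent-communication tests also stop at T2 is likely but inferred.
- *The primary endpoint or its timepoint was switched.* No primary timepoint was set, so none can have been changed.
- *T3 data must exist, given the SAP's 2024 date.* The only early date is an IRB approval for an NIH Just in Time request, which is not a study start.
- *All information after week 16 is lost.* T3 is one assessment. With the past-month self-harm measure it would cover roughly weeks 48–52, and would not observe the continuing-care weeks themselves.

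**Conclusion.** The point holds in two parts. It is certain from the text that the SAP states no inferential arm comparison of self-harm, and that it leaves a scheduled 12-month assessment unexplained. It is a likely inference that the other outcome analyses also end at T2. Whether T3 was collected cannot be determined from the documents.

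The repair should be required because it concerns the only primary endpoint and the efficacy aim, and because the T2 contrast is cheap. Its yield should not be oversold. Under the stated assumptions the self-harm interval is about ±16 to ±23 points with 35–50 per arm, and up to about ±28 with 25. No completer count is given, so the actual T2 precision cannot be placed in that range. Moderate effects may well be inconclusive, and an inconclusive T3 result would not show that no effect lasts.

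**What to change.** 1. **In every case:** report the between-arm difference in self-harm at T2 with a 95% CI, using the past-month measure. Adjust for baseline past-month self-harm or frequency if it was collected.
2. **If T3 was collected:** add arm contrasts with 95% CIs at T3 for self-harm and the secondary scores. Use a linear mixed model for scores. For self-harm, model T2 and T3 as responses with baseline as a covariate. Do not use the 6-month self-harm item as a baseline response: section 5 makes it an entry criterion, so it equals 1 for everyone. Label these as added analyses and give completers per arm.
3. **If T3 was not collected or is deferred:** say so with the reason, and limit conclusions to end of treatment.

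Cost: if T3 is unavailable, one SAP paragraph and one contrast. If it is available, more analysis but no new data collection. The downsides are more comparisons, the post hoc status of the additions, wide intervals, and reliance on missing at random.

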## 5) Inclusion and Exclusion Criteria\*

Inclusion Criteria: To be included in the study, the adolescent must: (a) be 11 to 18 years old; (b) self-report an act of self-harm in the past 6 months, (c) meet cut-off criteria on two of the four maintaining factors (depression, emotion dysregulation, family conflict, substance use), and (d) live with at least one parent-figure who agrees to participate in assessments and treatment. Participants should be willing and able to participate fully in the protocol (e.g., to accept assignment to either condition, to provide sufficient locator information for follow-up, to allow their treatment sessions to be recorded for fidelity/process assessment and supervision). All family members in the household are invited to participate in treatment. Our success at engaging family members is evident in that an average of three family members per household participated in family intervention studies.

Exclusion Criteria: Exclusion criteria include: (a) history of DSM V Developmental Disorders, Elective Mutism, Organic Mental Disorders, Schizophrenia, Delusional Disorder, Psychotic Disorder, and Bipolar Affective Disorder. We will exclude youth who are actively in crisis and reporting current ideation with a specific plan and with means to complete the plan. If a youth is referred in this state, it will be a priority to utilize a warm-handoff procedure to connect them to a more intensive treatment program.

Eligibility Screening: Staff at the referral sites will be trained to identify youth appropriate, namely a self-harm event, for the study. When a youth/family is identified as potentially appropriate the referral site will ask the family to sign a release of information so that study personnel can contact them to schedule a formal screening. If the form is signed, the referral site will contact the designated study personnel (assessor) and provide the contact information for the family. The study personnel will contact the family and schedule an appointment to conduct the screening. When the family attends the appointment, the screening measures (Self-harm, family conflict, emotion dysregulation, depression and substance abuse) will be administered to determine eligibility. (see sections below)

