NCT03709472

Computer Assisted Family Intervention to Treat Self-Harm Disparities in Latinas and Sexual/Gender Minority Youth

Statistical Analysis Plan 8/21/24

Data were analyzed using SPSS Version 29 (IBM, 2023). We began our analyses by documenting the number of session and hours of treatment to assess CIFFTA's feasibility and acceptability. We conducted logistic regressions to examine whether baseline characteristics predicted those participants who successfully reached termination and T2 assessments. To examine whether changes in adolescent symptoms of depression over time differed by treatment, a mixed ANOVA was used with depression scores as the within-subjects variable and treatment condition as the between-subjects variable. We used the same analytic strategy to determine whether changes in emotion regulation and family connectedness differed over time by treatment. A series of mixed ANOVAs were used with the Total scores from the PHQ-9, the Difficulty with Emotion Regulation Scale and the Family Connectedness Scale as the within-subjects variables and treatment condition as the between-subjects variable. When effect sizes are reported, cutoffs for partial eta-squared effect sizes are small .01, moderate .06, large .14. Additionally, Chi-Square Tests of Association were used to determine whether the proportion of youth endorsing whether they could talk to their parent about problems differed over time. This analysis was conducted by condition examining mothers and fathers separately.

A complementary analytic strategy was used to investigate change in youth who entered the study with presenting problems in the clinical range at baseline assessments based on established clinical cutoffs (i e., those with at least mild levels of depression at baseline). Descriptive statistics were used to determine the rates of suicidal thoughts and self-harm at baseline and termination by condition. In addition, Chi-Square Tests of Association were used to determine whether the proportion of youth endorsing thoughts of suicide differed by treatment condition.

We also used the Reliable Change Index (RCI) to determine whether the magnitude of change was statistically reliable rather than due to random fluctuations caused by measurement error (Jacobson & Traux, 1991). We examined symptoms of depression.

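### The exploratory mechanism regressions pool both arms without a treatment term, so an effect of treatment on both the mechanism and self-harm can look like a mechanism

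*SAP*

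**What the plan says.** The SAP's final paragraph describes a series of hierarchical logistic regressions in which "self-harm in the past month was the binary outcome variable". The analysis is made "at termination in the full sample; after controlling for gender and LGBTQ status", so the two arms are pooled. For adjustment, "LGBTQ status and gender were entered in Step 1 as covariates"; nothing else is listed for that step. After that, "the proposed mechanism of action (i.e., depression, parent communication, family connectedness, and emotion regulation) were entered in Step 2". The aim sentence speaks of changes in the mechanisms, but the model sentence does not say whether Step 2 takes a change score or the termination level.

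On mediators, the SAP limits its own claim: "With only two timepoints we could not conduct formal analyses of mediation, but we could explore whether the patterns of change were consistent with plausible" ones.

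The omitted variables are available. Earlier in the SAP, "Descriptive statistics were used to determine the rates of suicidal thoughts and self-harm at baseline and termination by condition", so condition and baseline self-harm are both in the dataset. Eligibility does not make baseline self-harm constant. Protocol section 5 requires youth to "self-report an act of self-harm in the past 6 months", whereas the model's outcome covers the past month.

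**The concern.** Aim 2 (protocol section 3) looks for a treatment effect on self-harm and also on the factors behind it. CA CIFFTA has many components (protocol section 10), so it could reduce self-harm by one route and improve, say, family connectedness by another. In the pooled sample, treated youth would then show both more improvement on connectedness and less self-harm. A model without arm reads that as a link between the two. The problem arises when the treatment works, which is when readers will most want to know why.

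Baseline past-month self-harm raises a similar question. It probably predicts self-harm at termination, and it may be related to the mechanism score.

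At stake is how far a significant Step 2 term can be read as fitting a plausible mechanism.

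**Working it through.** The documents give no effect size, event rate, significance level or power figure for this analysis, so there is no stated figure to reproduce. Every effect below is an assumption.

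**Inputs**
- Sample size: 100 randomised (protocol section 6). The n = 70 case borrows the roughly 70% adolescent assessment rate that section 10 reports for an earlier trial at 16 months.
- Allocation: 1:1, assumed from the coin-flip description in section 30.
- Test: likelihood-ratio test of one mechanism in Step 2 over Step 1, two-sided 5% (assumed).
- Truth in every scenario: the mechanism has no effect on self-harm.

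**Step 1. Hand approximation for the missing arm term**

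If arm is the only link, the correlation induced between mechanism and self-harm is about r = r1 × r2, where
- r1 (arm, mechanism) = d / √(d² + 4);
- r2 (arm, self-harm) = ½(pC − pT) / √(p(1 − p)), with p the mean of the two rates.

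The test statistic is centred near z = r√n, and the rejection rate is P(Z > 1.96 − z) + P(Z < −1.96 − z).

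For d = 0.8 and self-harm 25% v 50% at n = 100:
- log OR = ln[(0.25/0.75)/(0.50/0.50)] = −1.10
- r1 = 0.8/√4.64 = 0.371
- r2 = 0.125/√(0.375 × 0.625) = 0.258
- r = 0.371 × 0.258 = 0.096, so z = 0.96
- rejection rate = 0.158 + 0.002 = 16.0%

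**Step 2. Simulation (3,000 trials per scenario) beside the approximation**

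| Mechanism d | Self-harm, treated v control | log OR | n | Hand | Simulated, as planned | Simulated, arm added |
|---|---|---|---|---|---|---|
| 0.5 | 30% v 50% | −0.85 | 100 | 7.8% | 7.8% | 5.6% |
| 0.5 | 30% v 50% | −0.85 | 70 | 7.0% | 8.0% | 5.8% |
| 0.8 | 25% v 50% | −1.10 | 100 | 16.0% | 16.8% | 5.6% |
| 0.8 | 25% v 50% | −1.10 | 70 | 12.6% | 14.1% | 6.4% |
| 0.8 | 20% v 60% | −1.79 | 100 | 32.9% | 35.2% | 5.0% |
| 0.8 | 20% v 60% | −1.79 | 70 | 24.5% | 27.3% | 6.2% |

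Nearly all of the as-planned rejections lie in the direction of a mechanism (for example 16.6 of the 16.8 points in the third row).

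Further simulation sets with d 0.5 to 0.8 and log OR −1.0 to −1.4 gave 8-16% and 9-19% at n = 70, 8-18% and 10-22% at n = 100, and about 9-24% in the widest set. With arm in the model the rates were about 5-7%.

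**Step 3. When there is no inflation**

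If r1 or r2 is zero, r is zero. The simulations agree: 5.2-6.3% when arm affects only the mechanism or only self-harm.

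**Step 4. Baseline self-harm omitted, no arm effects**

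Assume an odds ratio of 4 for baseline on later self-harm, and baseline mechanism scores 0.6 SD worse in youth who self-harmed. At n = 100:
- change scores in Step 2: 9.1% rejections, only 0.8% in the direction of a mechanism, because regression to the mean pushes the other way;
- termination levels in Step 2: 8.4%, of which 7.7% in the direction of a mechanism.

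A different assumption, that youth who self-harmed at baseline improve 0.5-0.8 SD less (log OR 1.5 for baseline self-harm), combined with the arm effects, gave 19-27% at n = 70 and 22-35% at n = 100. The result turns on the assumption and on what Step 2 enters.

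**Step 5. What the adjustment cannot remove**

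Assume an unmeasured improvement at termination that drives both variables (odds ratio 2 per SD). At n = 100 the rejection rate is 34.4% as planned, 34.0% with arm, and 44.3% with arm and both baselines. At n = 70 it is 27.8%, 27.7% and 34.0%.

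**The case against.** The strongest reply is that the SAP already disclaims formal mediation, calls the work exploratory and asks only about association. That stands, and it limits the seriousness of the point. A reader might infer that these models are the trial's statement of how CIFFTA works. No section says so, and none of the four aims is a mediation aim. But the caveat rests on having two timepoints, and two timepoints do not prevent adjustment for arm and baseline. An association produced by arm tells nothing about whether the pattern fits a plausible mediator.

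A reader might also infer that the models will show mechanisms where none exist. The figures do not support that. Inflation needs separate effects on both variables, and even in the most extreme row of the table about 65% of null tests stay non-significant (100 − 35.2).

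Third, the baseline half of the point is weaker than the arm half. It is tempting to say that omitting baseline self-harm favours a false mechanism. With change scores the bias can run the other way, and the model sentence does not say which form is used.

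Last, the adjustment is no cure. Mechanism and outcome are taken at the same visit, so a shared concurrent cause is at least as plausible as confounding by arm, and Step 5 shows that it remains. The rate even rises with the baseline terms, probably because they take noise out of the change score. This is a reason to word the result cautiously, not a reason to leave arm out.

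**Conclusion.** The point holds in a limited form. The missing arm term can produce a mechanism-like association when treatment affects both variables by separate routes: about 8-24% false positives per test at n = 70 to 100 for d 0.5 to 0.8 and log OR −1.0 to −1.4, up to 35% at the larger effects in the table, and about 5-7% once arm is in the model. These figures rest on assumed effects, event rates, allocation and significance level. They are per test; four independent tests at 5% already give 1 − 0.95⁴ = 18.5% for at least one false positive without any confounding.

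Omitting baseline self-harm is a further possible bias of uncertain size and direction. The documents do not support the inference that adding arm and baseline would turn these regressions into evidence of mechanism. The change is a cheap improvement to an exploratory analysis and does not bear on the treatment comparison itself.

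**What to change.** 1. In Step 1 of each model, enter treatment arm with gender and LGBTQ status, and add baseline past-month self-harm and the baseline value of the mechanism. Use Firth penalised likelihood if events are few.
2. State that Step 2 enters change scores.
3. Report each Step 2 odds ratio with its 95% CI, described as an association adjusted for arm and baseline.
4. Keep the statement that this is not a mediation analysis. Add that mechanism and outcome are measured at the same visit, so shared concurrent causes remain and this adjustment does not remove them.

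Cost: all the variables are already collected. The SAP is dated 8/21/24 and written in the past tense, so the change means re-running and re-reporting these models as well as new wording. Up to three more terms in a small logistic model will widen the intervals; Firth likelihood reduces small-sample bias but does not restore that precision.
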